Section 2.0 Introduction:

The novel coronavirus, now officially designated as severe acute respiratory syndrome coronavirus-2 or SARS-CoV-2 was first identified in Wuhan, Hubei Province, China in December of 2019. Since its identification, Coronavirus disease 2019 (COVID-19) has evolved into an international public health emergency. As is common for the coronavirus family, (SARS-CoV-1 and MERS), COVID-19 is associated with acute respiratory infection. The mortality of COVID-19 infection is mostly due to complications related to pneumonia and ARDS¹.

Strategies to mitigate ARDS and consequent multi-organ failure is in high demand. Currently, there are no FDA-approved treatments outside of supportive care for patients suffering from ARDS due to COVID-19. Unique to COVID-19 associated respiratory failure and ARDS is the early overproduction of proinflammatory cytokines. This exaggerated immune response or “cytokine storm,” is felt to lead to increased vascular hyperpermeability, multiorgan failure, and death. Many ARDS/lung injury patients manifest refractory hypoxia, cardiac arrhythmias and acute myocardial damage¹⁰⁻¹³. Cardiovascular complications such as circulatory failure are

frequently associated with COVID-19 ARDS and are associated with a poor outcome¹⁴. Case series have noted cardiac arrhythmias, cardiomyopathy, and cardiac arrest as terminal events in Covid-19¹⁵⁻¹⁷. Stellate ganglia block (SGB) is a common clinical intervention to treat both sympathetic nervous system overstimulation and refractory cardiac arrhythmia. Traditional chemo-neuromodulation paradigms employ a single SGB strategy deriving short-term (lasting a few hours to one day) control of sympathetically mediated symptoms, e.g., cardiac arrhythmias are controlled by temporarily blocking stellate neuronal activity with local anesthetics¹⁸⁻²⁰. Once the anesthetic effect is withdrawn, cardiac arrhythmias recur. We propose a modified SGB strategy utilizing a continuous infusion of medications instead of a bolus injection. We expect to achieve a lasting chemo-neuromodulating effect in COVID-19 ARDS patients reducing overall inflammation, improving pulmonary function, and reducing cardiac complications.

Preliminary Data: A notable innovation of our modified SGB approach is the addition of clonidine and dexamethasone to a local anesthetic (LA). The scientific rationale supporting this modification is derived from both the literature as well as work done here at UNMC by [name] (Figure 1).

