The attending proceduralist will perform the SGB in the ICU/progressive care. ICU/progressive care nurse will provide patient monitoring and assistance during the procedure. Standard monitors and ACLS resuscitative equipment will be immediately available. A norepinephrine solution will be at bedside to treat potential hypotension associated with SGB. The SGB perineural catheter will be placed using standard sterile technique. Initial perineural bolus injection - clonidine 100 mcg, Decadron PF 5mg, and 0.25% bupivacaine 5 ml is delivered. A Cadd perineural infusion 0.2% bupivacaine will be initiated at 2ml/hr for 5 days. Acute pain service will discontinue infusion and remove the catheter after 5 days.

All adverse events and serious adverse events related to the SGB. All other adverse and serious adverse events, including death will be reported per IRB requirements. Laboratory analysis will be obtained at baseline (prior to block, baseline) and on day 1, day 3, and day 5. Labs include a cytokine panel (TNF-beta, IL-6, and IL-1 β), measurements of exhaled nitric oxide levels, and CRP (daily). Vital Parameter Analysis: Oxygenation, supplemental oxygen, type of respiratory support and need for mechanical ventilation, blood pressure i.e. hypotension requiring vasopressors and utilization of ECMO, heart rate, heart rhythm/new dysrhythmias, ICU/progressive care length of stay and discharge disposition will be collected from the EMR.

Control group: There will be no sham procedure for the control group. The control group will have nitric oxide levels performed once a day by a member of the research team. Lab draws will be drawn at the same frequency as the treatment group.

Treatment group:

The treatment group will have a SGB placed by the APS.

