Appendix A. Protocol for stellate ganglion blockade in COVID-19 patients.

ICU/progressive care RN will follow Med-27 NM policy for peripheral nerve catheter management. APS will utilize a similarly established standard of care in managing the catheters daily, for 5 consecutive days. This includes daily rounding on the patient to assess for signs of infection, muscle weakness, voice hoarseness, hematoma, intravascular migration, local anesthetic systemic toxicity, correct medication verification, verification of pump setting, evaluation for Horner's syndrome (expected), patient education, and proper dressing coverage.

Horner's syndrome refers to a constellation of symptoms that are associated with a stellate ganglion block. These include a decreased pupil size on the affected side, delayed reaction to light on the affected side, drooping eyelid and decreased sweating on the affected side. Increased temperature and vascular dilation are also noted on the affected side with stellate ganglion block.

Schedule of events: *treatment group only

Assessment	Screening: Visit-1	Baseline, Enrollment, Randomization : (Day 0)	Treatment Day 1	Treatment Day 2	Treatment Day 3	Treatment Day 4	Treatment Day 5	EOS Discharge from hospital	Follow-up: Day 90
Inclusion/Exclusion Criteria	X								
Informed Consent Form	X								
Enrollment/Randomization	X								
Demographics	X								
Eligibility	X								
Medical History	X								
Data Collection (Vitals ect)	X	X	X	X	X	X	X	X	
Acute Pain Service		X*	X*	X*	X*	X*	X*		
Stellate Ganglion Block		X*							
CRP		X	X	X	X	X	X		
TNF-Alpha		X	X		X		X		
IL-Beta		X	X		X		X		
IL-6		X	X		X		X		
Nitric Oxide Level		X	X	X	X	X	X		
Telephone Call									X
Concomitant Medications		X	X	X	X	X	X	X	X
Adverse Events		X	X	X	X	X	X	X	X

Section 6.0 Measurement of Effect:

We will be taking *measurement of the biomarkers indicative of oxygenation, lung and proinflammatory immune response and nitric oxide* - specifically,

[figure not shown]
- a) differences in mean/median values for SGB vs SOC will be assessed at each of the study designated time points for all the continuous biomarker measures - by assessing magnitude of difference and its 95% confidence level and testing differences for statistical significance at each of the time points;

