- b) Differences in mean/median values for SGB vs SOC will be assessed at treatment day 5 - adjusted for baseline levels
- c) Differences in changes from baseline levels for SGB vs SOC as measured by comparison in slope trends;
- d) Differences in frequency of adverse events for SGB vs SOC over the study period from treatment through 90 day of follow up;

Secondarily,

- e) Differences between SGB vs SOC in *frequency and time to occurrence of cardiac arrhythmias*;
- f) Differences between SGB vs SOC in frequency of *need for and duration of use mechanical ventilation and/or extracorporeal membrane oxygenation (ECMO)*;
- g) Differences between SGB vs SOC in survival experience over treatment period through 90 -day discharge follow up

Sample Size issues:

For power computations we assume that SGB will particularly have an impact in reduction of inflammatory response as measured by IL-6. Looking at a meta-analyses of IL-6 values [Ulhaq ZS, Soraya GV. Interleukin-6 as a potential biomarker of COVID-19 progression. *Med Mal Infect.* 2020;50:382–383. doi: 10.1016/j.medmal.2020.04.002. 2020/04/08] and picking the largest of studies of COVID patients [Qin C, Zhou L, Hu Z, Zhang S, Yang S, Tao Y, et al. Dysregulation of immune response in patients with COVID-19 in Wuhan, China. *Clin Infect Dis* 2020, <http://dx.doi.org/10.1093/cid/ciaa248> [pii: ciaa248].], we estimate the overall mean (SD) IL-6 for COVID-19 patients to be 21 pg/mL (30.1). Using these estimates we see that a sample of 16 patients equally randomized into SGB (n=8) and SoC (n=8) would provide sufficient power to observe magnitude of differences in mean of IL-6 from as small as about 50 pg/mL and larger with 80% power at the 5% significance level assuming 2-sided hypothesis testing. (see Power Figure). The study [Liu MH, Tian J, Su YP, Wang T, Xiang Q, Wen L. Cervical sympathetic block regulates early systemic inflammatory response in severe trauma patients. *Med Sci Monitor.* 2013;19:194–201.], indicates that SGB is capable of eliciting reductions of IL-6 between groups and from baseline of magnitudes of greater than 100 pg/mL within 72hrs of first injection.

Section 7.0 Study Parameters:

Baseline Assessments

- Current Fio₂/PaO₂ ratio
- Current type of ventilation and oxygen use
- Current production of nitric oxide via Niox
- Current blood pressure and heart rate parameters
- Labs: IL-1beta, TNF-alpha, IL-6, ABG, CRP
- Chest x-ray
- Need for mechanical ventilation or other support

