Initial perineural bolus injection will include clonidine 100 mcg, decadron PF 5mg, and 0.25% bupivacaine 5 ml.

Perineural catheter:

Infusion of 0.2% bupivacaine will be initiated at 2ml/hr for 5 days.

All medications are FDA approved. Standard orders for perineural blocks will be entered into the EMR system. Pharmacy responsible for ICU/progressive care will dispense orders for the medication used in the SGB. Pharmacist in ICU/progressive care will fill Cadd pump infusion catheter once per day per standard procedure in the ICU/progressive care.

Section 9.0 Adverse Event Reporting Guidelines:

The initial procedure will be stopped and the patient will be withdrawn if any of the following occurs; vasopressor or unresponsive hypotension, intrathecal injection, pneumothorax, expanding hematoma, allergic reaction, or cardiac arrhythmias. For continuous infusions, the catheter will be removed and the patient will be withdrawn if any of the following occur: local systemic toxicity, seizure, catheter migration to intravascular or intrathecal space, expanding hematoma, vasopressor unresponsive hypotension, symptomatic bradycardia, insertion site infection. Any adverse events will be treated with Nebraska Medicine standard of care procedures. Subjects can also voluntarily withdraw at any time. The PI can also withdraw any subject that is not felt to be a suitable candidate for the study.

Serious adverse events directly related to block will result in withdrawal. Directly block related serious adverse events include: local systemic toxicity, seizure, serious allergic reaction, expanding hematoma, or catheter migration to intravascular or intrathecal space, insertion site infection. As well, patients will be withdrawn if the patient develops medication unresponsive bradycardia or hypotension. This may not be directly related to block but discontinuation of infusion may facilitate resuscitation of patient. Expected complications may include voice hoarseness, ipsilateral eyelid drooping, mild pain at site of catheter, and blurred vision. Occurrence of expected complications will not result in withdrawal from study unless demanded by the patient.

Section 10.0 Statistical Considerations:

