Statistical considerations for primary objective, the analysis would include means/medians (standard errors, IQRs) at each time point - and also represented by error bars - and comparisons using t test or the Mann-Whitney U test as appropriate. Multivariate analyses using Generalized estimating equations (GEE) and to compare longitudinal changes in the two groups adjusting for confounders and as well as ANCOVA based regression to measure before and after changes. Kaplan-Meier survival methods to measure time to defined thresholds and Cox regression to assess any impact of confounders.

For safety - AE's will be assessed by providing descriptive statistics related to their frequency (summarized by occurrence, percentage of occurrence, severity, seriousness, outcome, relation to treatment, start time summary, duration of AE analysis) as well as graphically via box plots and cumulative incidence plots indicative of distributions in the two trial groups. Non-parametric methods (e.g. Fisher Exact testing) will be used to statistically compare the period frequency of events between the two groups. In general, timely analysis, by creating summaries of adverse events and other safety measurements such as relevant vital signs, ECG, Laboratory abnormal findings will be done to keep a check on the increase in intensity of observations taken at baseline and/or new findings arisen after baseline.

Secondary measures:

Occurrence of cardiac arrhythmias, need for mechanical ventilation and/or ECMO as well as overall survival will be compared using time-to-event based methods (e.g. Kaplan-meier curves). The expectation is that any non-statistically significant but implied trends will be evaluated in larger phase IIb /III trial that will follow.

Stopping Rules:

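### Section 6.0 adjusts for baseline only at Day 5 and measures change from baseline by slope, although IL-6 is also sampled on Days 1 and 3 and the cited IL-6 evidence lies within 72 hours

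*Combined protocol and SAP*

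**What the plan says.** Section 6.0 lists three comparisons for the continuous biomarkers.

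- Item (a) gives the between-arm difference with a 95% interval, and includes "testing differences for statistical significance at each of the time points". No baseline adjustment is mentioned.
- Item (b): "Differences in mean/median values for SGB vs SOC will be assessed at treatment day 5 - adjusted for baseline levels". Day 5 is the only time point named.
- Item (c): "Differences in changes from baseline levels for SGB vs SOC as measured by comparison in slope trends".

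Section 5.0 sets the cytokine sampling: "Laboratory analysis will be obtained at baseline (prior to block, baseline) and on day 1, day 3, and day 5". The schedule of events agrees for IL-6.

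The sample size text in Section 6.0 rests on IL-6. It cites a study of sympathetic block in trauma patients, with reductions between groups and from baseline "of magnitudes of greater than 100 pg/mL within 72hrs of first injection". With the block placed on Day 0, that window closes at about the Day 3 sample.

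Section 10.0 plans t or Mann-Whitney comparisons with summaries at each time point. It also plans GEE "to compare longitudinal changes in the two groups adjusting for confounders and as well as ANCOVA based regression to measure before and after changes". It does not state how time is coded in the GEE, whether baseline is a covariate, or at which visits the ANCOVA applies.

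On exposure, Section 2.0 says: "We propose a modified SGB strategy utilizing a continuous infusion of medications instead of a bolus injection". Section 8.0 says: "Initial perineural bolus injection will include clonidine 100 mcg, decadron PF 5mg, and 0.25% bupivacaine 5 ml", followed by a 5-day infusion for which only bupivacaine is listed. Section 5.0 and Appendix A match Section 8.0.

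**The concern.** The plan collects a baseline IL-6 value and relies on evidence from the first 72 hours. Its two baseline-based comparisons look elsewhere. Item (b) looks at Day 5, and item (c) compresses four time points into one straight line. A line fitted over Days 0, 1, 3 and 5 gives Day 5 the largest weight, and gives Day 1 a weight of the same sign as baseline. An early fall that has partly or wholly recovered by Day 5 therefore scarcely moves it. A step down that is then held is also summarised inefficiently.

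At stake is how clearly an early effect would show. With 8 patients per arm, the Day 1 and Day 3 comparisons forgo the precision that baseline could add. The three items could also point in different directions, and the plan does not say which one leads.

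**Working it through.** **Inputs from the documents.** 8 vs 8 patients; IL-6 mean 21 and SD 30.1 pg/mL; difference of about 50 pg/mL; two-sided 5%; 80% power (Section 6.0). Sampling at Days 0, 1, 3 and 5 (Section 5.0).

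**Assumptions.** Normal data, the same SD at every visit, and a within-patient correlation r of 0.3, 0.5 or 0.7, equal for all pairs of visits. The documents give no correlation. Item (c) is taken as a t test on per-patient least-squares slopes.

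**1. The plan's own figure.** SE of the difference = 30.1 × √(2/8) = 15.05. For 50 pg/mL the noncentrality is 50/15.05 = 3.32 on 14 df, which gives 87.0% power. The difference detectable with 80% power is 45.3 pg/mL by t test. The stated value of about 50 is reproduced and slightly conservative.

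**2. Item (a) at Day 1 or Day 3.** This is the same test, so it has about 87% power for 50 pg/mL on either day.

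**3. Slope weights.** The mean time is 2.25 and the sum of squares is 5.0625 + 1.5625 + 0.5625 + 7.5625 = 14.75. Weight = (t - 2.25)/14.75:

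| Day | 0 | 1 | 3 | 5 |
|---|---|---|---|---|
| Weight | -0.153 | -0.085 | +0.051 | +0.186 |

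The SE of the slope difference is 30.1 × √((1 - r)/14.75) × √(2/8), which is 3.28, 2.77 and 2.15 pg/mL/day for r = 0.3, 0.5 and 0.7.

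**4. Expected slope difference (SGB minus SOC)** for effects on Days 1, 3 and 5:

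- -25, -50, 0: (-25)(-0.0847) + (-50)(0.0508) = -0.42 per day.
- -50, -50, 0: (-50)(-0.0847) + (-50)(0.0508) = +1.7 per day, the wrong direction.
- -50, -50, -50: 1.7 + (-50)(0.1864) = -7.6 per day.

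**5. Power by scenario.** ANCOVA figures are from simulation (20,000 trials per case), except in the first row, where there is no Day 5 effect and the power is the 5% test level. Ranges run over r = 0.3 to 0.7.

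| Effect on Days 1, 3, 5 | (a) Day 3, unadjusted | (b) Day 5 ANCOVA | (c) slope |
|---|---|---|---|
| -25, -50, 0 | 87% | about 5% | about 5% |
| -50, -50, 0 | 87% | about 5% | 8% to 11% |
| -50, -50, -25 | 87% | 35% to 55% | 14% to 25% |
| -50, -50, -50 | 87% | 87% to 98% | 58% to 91% |

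**6. Gain from adjusting Day 3.** The residual SD falls to about 30.1 × √(1 - r²) = 28.7, 26.1 and 21.5. Simulated ANCOVA power at Day 3 for 50 pg/mL is 87%, 93% and 98%. Against 87% unadjusted, the gain is about 0, 6 and 11 points. The Day 1 results are the same.

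**7. The opposite case.** For an effect that builds up (-10, -30, -50), the slope has 82% to 99% power and Day 5 ANCOVA 88% to 98%, against 47% to 70% for Day 3 ANCOVA. The Day 5 comparison should therefore stay.

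**The case against.** A reader might infer that a transient effect would be reported as no effect. The documents do not support that.

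- Item (a) tests every time point and has about 87% power at Day 3 for the plan's own difference.
- Section 10.0 adds GEE and ANCOVA, neither limited to Day 5. A GEE with categorical visits would fit the present wording.
- Nothing in the documents says that the IL-6 effect fades by Day 5. The cited reduction occurred within 72 hours, and what followed is not described. Section 2.0 expects a prolonged effect, and bupivacaine runs for 5 days. The 5% figures arise only where the Day 5 effect is set to zero.

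All of this stands. Nor does it follow from clonidine and dexamethasone being listed only in the initial bolus that the IL-6 effect is over by Day 5. The infusion wording in Section 2.0 is a separate documentation point and does not bear on the power argument.

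It is also fair to say that chance baseline imbalance (SE 15.05 pg/mL, 95% range ±29.5) is not bias under randomisation and is already counted in the 87%. Adjustment buys precision; it does not rescue an invalid test. Replacing the slope by an area under the curve would be a trade-off: for the effect that builds up, at r = 0.5, power would be about 71% against about 92%.

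Two things remain. No baseline-adjusted comparison at Day 1 or Day 3 is named, and Section 10.0 is too open to supply one. The slope is also the weaker summary under the plan's own expectation of a lasting effect if onset is prompt: 58% to 91%, against 87% to 98% for Day 5 ANCOVA.

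**Conclusion.** The point holds as a gap in specification. Items (b) and (c) do not target the 72-hour window that supports IL-6, and taken alone they would largely miss an effect gone by Day 5. Item (a) would still test such an effect at Days 1 and 3, without stated baseline adjustment. The practical loss at Day 3 is therefore modest, about 0 to 11 power points depending on the correlation.

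The powers are illustrative. They assume normal data with a constant SD, whereas an SD of 30.1 against a mean of 21 suggests skewed IL-6. A fall of 50 pg/mL also exceeds that mean; the effect size is the plan's, used here for comparability. The slope weights assume a straight-line fit, which the plan does not spell out.

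**What to change.** - **Item (b):** apply the baseline-adjusted comparison (ANCOVA) at Days 1 and 3 as well as Day 5.
- **Item (c) and Section 10.0:** fit the GEE already planned with visit as a categorical factor, baseline as covariate and a group-by-visit term. Keep the slope as a supplementary summary only.
- **Separately:** reconcile the Section 2.0 description of the infusion with Sections 5.0 and 8.0, so that the report names the exposure actually given.

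The statistical changes are wording only, use samples already scheduled, and keep Day 5 for a late effect. Item (a) already tests each visit, so adjusted tests at Days 1 and 3 add no new time points. The text should say which version leads at each visit. With 16 patients, the GEE will need a small-sample correction to its robust standard errors.

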Available research indicates that an exaggerated immune response plays a key role in the cardiopulmonary pathophysiology of COVID-19. Preliminary data from previous studies at UNMC suggest that acute lung injury initiates robust and sustained macrophage activation in thoracic dorsal root ganglia and in stellate ganglia, resulting in increased cardiac and pulmonary afferent and efferent neuronal sensitivity. In the current proposal, we plan to validate a novel therapeutic strategy to treat coronavirus-induced cardiopulmonary symptoms and complications by local delivery of bupivacaine, dexamethasone, and clonidine to the stellate ganglia. Single injection and continuous infusion SGB have been safely utilized clinically and in many human studies.

Section 3.0 Eligibility Criteria:

Inclusion:

- Subject admitted to COVID ICU/progressive care, age 40-75 years old

Subjects must have + covid test with signs of impending respiratory compromise as identified by having at least 2 of the following:

- Respiratory rate ≥ 30 breaths per min
- Oxygen saturation at rest $\leq 93\%$
- $\text{PaO}_2/\text{FIO}_2 \leq 200$ mm Hg
- bilateral infiltrates on chest radiograph or CT not due to cardiac failure
- Requiring non-invasive or invasive mechanical ventilation.

Any patient with a + covid test and any cardiac tachydysrhythmia (excluding sinus tachycardia) will be included regardless of respiratory status. (Note: The broader inclusion of patients who have cardiac tachydysrhythmia is based on our prior experience and other reported beneficial antiarrhythmic effects of SGB in this patient group.)

Exclusion:

- Hemodynamic instability (>2 vasopressors)
- Heart rate < 60 beats per minute
- Systolic Blood pressure of less than 80 mmHg
- pre-hospital diagnosis of heart failure or fluid overload
- anatomical inability to perform block
- prior sympathectomy
- Patient currently enrolled in another clinical trial for COVID-19 or respiratory distress/ARDS
- Uncorrectable coagulopathy
- ECMO already engaged
- On Nitric Oxide
- Pre-existing multi-organ failure (>2 organ systems)
- Allergic to dexamethasone, clonidine, or bupivacaine.
- If female, currently pregnant or breast-feeding.
- Investigators determine the subject would be too unstable to participate in the study intervention.

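### The 80% power claimed for an IL-6 difference of about 50 pg/mL does not follow from the only mean and SD the plan gives (21 and 30.1 pg/mL), so the power statement is unsupported as written

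*Combined protocol and SAP*

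**What the plan says.** All the power reasoning is in the combined protocol and SAP, Section 6.0, under Sample Size issues.

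- Direction of effect: "we assume that SGB will particularly have an impact in reduction of inflammatory response as measured by IL-6".
- Inputs, taken from a published study of COVID-19 patients: "we estimate the overall mean (SD) IL-6 for COVID-19 patients to be 21 pg/mL (30.1"; the last figure is the SD.
- Conclusion: "Using these estimates we see that a sample of 16 patients equally randomized into SGB (n=8) and SoC (n=8) would provide sufficient power" for a "magnitude of differences in mean of IL-6 from as small as about 50 pg/mL and larger with 80% power", two-sided at 5%.
- Support for the effect size: a study in severe trauma is cited for "reductions of IL-6 between groups and from baseline of magnitudes of greater than 100 pg/mL within 72hrs of first injection".

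Three other places bear on the point. Section 3.0 describes who is enrolled: "Subject admitted to COVID ICU/progressive care, age 40-75 years old". Section 2.0 says of the disease: "Unique to COVID-19 associated respiratory failure and ARDS is the early overproduction of proinflammatory cytokines". Section 10.0 plans "comparisons using t test or the Mann-Whitney U test as appropriate", and also ANCOVA and GEE. A Power Figure is cited but is not shown in the text available.

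**The concern.** The paragraph presents the 50 pg/mL threshold as a result of the 21 (30.1) estimates and applies it to a reduction. Taken together, these statements conflict, because a non-negative marker with mean 21 cannot fall by 50.

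This is the only power statement in the text and the only numerical reason given for 16 patients. Section 10.0 expects non-significant trends to be carried into a larger phase IIb/III trial. A null IL-6 result could then be read as coming from a comparison with 80% power, when the text does not establish that power for any reduction possible from its own mean.

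**Working it through.** **Inputs.** From Section 6.0: 8 per arm, mean 21, SD 30.1, two-sided 5%, 80% power, threshold about 50 pg/mL. Tests from Section 10.0: t test or Mann-Whitney.

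**1. Reproducing the plan's figure.** For a two-sample t test with 14 degrees of freedom, the noncentrality is d × √(8/2) = 2d, where d = difference/SD. Power of 80% needs d = 1.5066.

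- Detectable difference: 1.5066 × 30.1 = 45.3 pg/mL.
- At 50 pg/mL: d = 50/30.1 = 1.661, and power is 87%.
- The normal approximation gives 42.2 pg/mL. Mann-Whitney at its minimum asymptotic efficiency (0.864) gives 49.5 pg/mL.

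So *about 50* is acceptable arithmetic for SD 30.1. The mean does not enter the formula.

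**2. Setting the threshold against the mean.**

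- 50/21 = 2.38. From a control mean of 21, the largest possible fall is 21.
- If 21 is read as the pooled mean of two equal arms, the largest possible gap is 2 × 21 = 42 (42 versus 0). That is still below 50 and below 45.3.
- The trauma figure: 100/21 = 4.76. A fall of that size belongs to a different IL-6 scale from the one that supplied the SD of 30.1.

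**3. What the plan's own mean and SD support.** The coefficient of variation (CV) is 30.1/21 = 1.433. Assuming lognormal IL-6 with equal CV in both arms, log SD = √ln(1 + 1.433²) = 1.057. The ratio of geometric means detectable with 80% power by a t test on log IL-6 is exp(−1.5066 × 1.057) = 0.20. For log SD 0.8 it is 0.30, and for 1.5 it is 0.10.

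Simulated power, unadjusted, 8 per arm:

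| Reduction from 21 | t test, raw | t test, log | Mann-Whitney |
|---|---|---|---|
| 50% | 14% | 23% | 22% |
| 75% | 42% | 69% | 66% |
| 80% | 52% | 81% | 78% |
| 90% | 73% | 98% | 98% |
| 95% | 80% | >99% | >99% |

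For a halving, log-t power runs from 37% to 14% as log SD goes from 0.8 to 1.5.

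**4. If the enrolled patients have a higher control mean.** Power for a 50 pg/mL fall, lognormal, equal CV in both arms. The control means are assumptions, since the text gives none.

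| Control mean | CV 1.43: raw t / log t / Mann-Whitney | Control SD 30.1: raw t |
|---|---|---|
| 55 | 74 / 99 / 98% | 99.9% |
| 60 | 59 / 88 / 86% | 99.9% |
| 75 | 29 / 49 / 47% | 99.8% |
| 100 | 14 / 23 / 22% | 98.8% |

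The answer depends almost wholly on how the SD moves with the mean, and the text does not say.

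**The case against.** The strongest reply is that 21 is an overall COVID-19 mean, not a forecast for the control arm. Section 6.0 compares the arms at each time point, so a gap of 50 needs only a standard-of-care mean above 50. That is plausible in ICU or progressive-care patients if cytokines are overproduced, as Section 2.0 says. This stands, and it rules out any claim that a 50 pg/mL difference is impossible in this trial. It does not rescue the sentence, which derives its power from the 21 (30.1) estimates. The SD of 30.1 belongs to the same source as the 21, and no SD is given for a higher mean.

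The trauma study might be offered as evidence that large falls occur. It concerns another population on another scale, and the text gives no SD for it, so it cannot be paired with 30.1.

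Three further points have weight. The Power Figure is not visible and may hold other assumptions, so the finding concerns the text only. The figures above are for unadjusted tests, whereas the plan includes baseline-adjusted analyses; these could improve power by an amount that depends on a baseline correlation the documents do not give. And this is a small phase I/II proof-of-concept study, for which a formal power claim is not the whole rationale.

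A reader might go further and infer that the calculation is wrong, that the trial is shown to be underpowered for IL-6, or that 16 patients are too few. The documents do not support these readings. The formula reproduces, and under some plausible inputs power exceeds 98%.

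**Conclusion.** The point holds as a fault in the stated justification, and it should be fixed. The effect for which 80% power is claimed is 2.4 times the only mean given and cannot arise from that mean. This part is certain, since it rests only on printed numbers and on IL-6 not being negative.

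Whether the trial has 80% power for a 50 pg/mL fall is undetermined. The answer turns on a control mean and SD that the text does not state. On the plan's own mean and CV, 80% power is reached only for about an 80% reduction (log t, with Mann-Whitney close to it) or about 95% (raw t). Those figures assume lognormal data, equal CV in both arms and no baseline adjustment. The design and the safety monitoring are untouched.

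**What to change.** Stop presenting 80% power at 50 pg/mL as a consequence of mean 21 (SD 30.1), and stop using the trauma figure to support the effect size. Then do one of the following.

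(i) State a sourced control mean and SD, on one scale, for the ICU and progressive-care patients to be enrolled, with the power for reductions that are possible from that mean.

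(ii) State the detectable effect as a ratio, naming the test and the assumptions, for example:

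> Assuming lognormal IL-6 with the same log SD of about 1.06 in both arms (from mean 21, SD 30.1), an unadjusted t test on log IL-6 with 8 per arm has 80% power at two-sided 5% for a geometric mean ratio of about 0.20 (Mann-Whitney about 78%). For log SD 0.8 to 1.5 the ratio is 0.30 to 0.10. A halving has about 23% power by log t (22% Mann-Whitney, 14% raw t) at log SD 1.06, and 37% to 14% by log t over log SD 0.8 to 1.5. The planned baseline adjustment may improve this by an amount that depends on the baseline correlation.

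The cost is wording only: no added patients, samples, visits or analyses. The stated detectable effect will look less favourable under (ii), which also rests on the lognormal assumption. Option (i) requires finding a suitable source.
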